Official Title: Application of Transcranial Alternating Current Stimulation for Modulation of Sleep and Cognitive Performance

NCT03112902

June 6th, 2021

Statistical Analysis Plan: For each arm, we will perform a three-arm cross-over design to determine whether there is a significant group difference between each tES condition as measured in EEG power in 0.5-2 Hz frequency following tES using repeated measures ANOVA. Recruitment of 15 subjects, with cross-over intervention (*sample size* 15) will allow us to detect differences between groups with an effect size of Cohen's  $d = 1.2$ , power of 80%, and significance of 0.05. This is based on sample sizes and effect sizes reported with motor network tES. Planned secondary analyses of each arm will include scores of slow wave EEG coherence, slow and fast spindle numbers, total duration of each sleep stage, changes in slow wave coherence, changes in slow wave power, self reported sleep timing changes, changes in anxiety and depression (measured by HADS), changes in clinical global impression of change (CGIC), and cognitive performance data, including assessment of procedural memory, verbal (declarative) memory encoding, attention/working memory/visuospatial processing using repeated measures ANOVA of the data.

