The subjects will be assigned to one of three treatment groups (tACS nested, tACS single frequency, or sham) using block randomization. Computer-generated randomization will place each subject into one of the study groups initially, then cross each subject the each other condition subsequent sessions. The primary outcome measure is induced EEG power of slow wave sleep of 0.5-2 Hz measured immediately before and after each train of stimulation. To detect a significant change ($p<0.05$) of EEG power increase $\geq 20\%$ above sham, with a power of 0.80, a sample size of 15 subjects will be necessary, based on effect sizes from prior studies (7). Subjects will receive 1 session for each stimulation type, in a cross-over design with at least 1 week between each stimulation condition for wash-out. This will total to 3 sessions for each subject, with a total of 45 sessions for all subjects. Subjects will have up to 24 weeks to complete all study sessions and complete the trial. The proposed study seeks to enroll 30 participants to account for participants that may fail our screening criteria, have unusable data or drop-out of the study before completion. Secondary outcomes will include analysis of slow wave EEG coherence, sleep spindle signal, duration of slow wave sleep, total duration of sleep, word-paired associates task and finger tapping task (7, 25), as well as subjective sleep quality reported on the Consensus Sleep Diary and Pittsburgh Sleep Quality Index (38, 39). Data collection for this study is expected to take 6 months.

4. Assessment of tACS in Older Adult Subjects: In this branch of our study, we will test older adults for response to tACS applied during NREM sleep, with outcomes of EEG data, cognitive performance assessments, as well as assessment of sleep quality, mood, and quality of life measures. In addition, subjects will be screened for decisional capacity via the UCSD Brief Assessment of Capacity to Consent (UBACC), and subjects who are found to have impaired capacity will require a legally authorized representative for consent (40).

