The subjects will be assigned to one of two treatment groups (tACS nested , or sham) using block randomization. Computer-generated randomization will place each subject into one of the study groups initially, then cross each subject the each other condition for subsequent sessions. The primary outcome measure is induced EEG power of slow wave sleep of 0.5-2 Hz measured immediately before and after each train of stimulation. To detect a significant change ($p<0.05$) of EEG power increase $\geq 20\%$ above sham, with a power of 0.80, a sample size of 15 subjects will be necessary, based on effect sizes from prior studies (7). Subjects will receive 1 session for each stimulation type, in a cross-over design with at least 1 week between each stimulation condition for wash-out. This will total to 2 sessions for each subject, with a total of 30 sessions for all subjects. Subjects will have up to 24 weeks to complete all study sessions and complete the trial. The proposed study seeks to enroll 35 participants to account for participants that may fail our screening criteria, have unusable data or drop-out of the study before completion. Subjects will also be required to have a study partner assist them at home during the adaptation night and treatment sessions. We are NOT collecting any information about the study partner, they are simply required to assist the subjects. Secondary outcomes will include analysis of slow wave EEG coherence, sleep spindle signal, duration of slow wave sleep, total duration of sleep, word-paired associates task and finger tapping task (7, 25), as well as subjective sleep quality reported

on the Consensus Sleep Diary and Pittsburgh Sleep Quality Index (38, 39). Data collection for this study is expected to take 6 months.

5. Assessment of tACS in MCI Subjects: In this branch of our study, we will test individuals with MCI for response to tACS applied during NREM sleep, with outcomes of EEG data, cognitive performance assessments, as well as assessment of sleep quality, mood, and quality of life measures. In addition, subjects will be screened for decisional capacity via the UCSD Brief Assessment of Capacity to Consent (UBACC), and subjects who are found to have impaired capacity will require a legally authorized representative for consent (40).

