All efforts will be made to protect the confidentiality of research subjects. All electronic data will be collected via REDCap, de-identified by the research team, and stored on their servers. Only study personnel will have access to the data. The dataset will be stored on a computer that is password-protected, virus-protected, and automatically logs the user off after a period of inactivity. The computer is located in a locked office. The computer will be password protected when not in use. All written data will be stored in a locked file cabinet in a private office, the research office of the Department of Neurology. All personnel involved in the study have completed HIPAA training. Any PHI will be stripped from data files (or shredded from written records) within 6 months of the end of the data collection period such that all PHI will be deleted prior to completion of the final data set. Any publication of data will be reported in aggregate.

XV. WITHDRAWAL OF PARTICIPANTS

Subjects will be withdrawn if they experience adverse effects due to tACS application or are unable to tolerate wearing of equipment. Data from subjects that withdraw will be collected and protected, but not utilized in the data analysis. Follow up will only be performed in the case of adverse events to ensure the safety of the patient.

XVI. RISKS TO PARTICIPANTS

tACS

Over 10,000 research subjects had received tES, including tACS, as of 2014, without any serious side effects reported (51). There has been no evidence of seizures, neuronal pathology, edema or neuropsychological damage (15). At-home, unsupervised, application of tES has been demonstrated to be safe and well-tolerated, without any major adverse events or safety concerns (26, 27). During administration of tES, subjects have reported a mild tingling sensation (70.6%), moderate subjective fatigue (35.3%) and a light itching sensation (30.4%). After administration of tES, subjects have reported mild transient headaches (11.8%), nausea (2.9%) and insomnia (0.98%) (52). Our stimulation parameters (maximum current density 0.515 mA/cm²) are far below established safety thresholds of 14.29 mA/cm² (49). All stimulation parameters within this proposal are well below currently accepted safety guidelines for tACS (50).

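### A period term in the cross-over ANOVA, with the session order stated for the 18-50 branch, is a cheap gain in precision, not a repair of validity

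*SAP*

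**What the plan says.** The SAP's primary analysis tests for a "significant group difference between each tES condition as measured in EEG power in 0.5-2 Hz frequency following tES using repeated measures ANOVA". Neither document names a period, session or sequence term.

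**18-50 branch (Protocol IV.3).** There are three conditions. The start is block-randomised, and then: "Computer-generated randomization will place each subject into one of the study groups initially, then cross each subject the each other condition subsequent sessions". With three conditions the start does not fix the order of the other two.

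**Older-adult branch (Protocol IV.4).** "The subjects will be assigned to one of two treatment groups (tACS nested , or sham) using block randomization", and "This will total to 2 sessions for each subject, with a total of 30 sessions for all subjects". Here the first session fixes the second, so sequences are balanced at allocation and only the model is at issue. This branch also has an adaptation night without stimulation; the 18-50 branch has only a daytime equipment trial.

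**Outcome.** Both branches of the protocol say: "The primary outcome measure is induced EEG power of slow wave sleep of 0.5-2 Hz measured immediately before and after each train of stimulation". The SAP's primary comparison is of power after stimulation, and its secondary list includes "total duration of each sleep stage, changes in slow wave coherence, changes in slow wave power".

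**Who is analysed.** Fifteen subjects are needed in each branch. For the 18-50 branch, "The proposed study seeks to enroll 30 participants to account for participants that may fail our screening criteria, have unusable data or drop-out"; the older-adult branch enrols 35. Protocol XV adds: "Data from subjects that withdraw will be collected and protected, but not utilized in the data analysis".

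**The concern.** A cross-over compares conditions given on different nights. If nights differ for reasons other than the condition (a poor first night in the equipment, or practice on memory tasks repeated every treatment night), a model without a period term has to put that variation somewhere.

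- If conditions are spread evenly over sessions, it goes into the residual. The test becomes conservative and power is lost.
- If they are not, part of it goes into the condition contrasts as bias.

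Which applies depends on the sequences, and in the 18-50 branch these are not fully stated. A before/after change within the same night would largely cancel an additive night effect. However, the SAP does not say whether its primary outcome is the after value or the change.

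**Working it through.** **The plan's own figure.** The SAP gives n = 15 for d = 1.2, 80% power and 0.05. A two-sided paired t-test with d in SDs of the difference needs 8, and at n = 15 its power is 0.99. Two independent groups need 2(1.960 + 0.842)²/1.2² = 10.9, so 11 per group (12 by t). The stated 15 is not reproduced and is generous for a cross-over; it does not bear on this point.

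**Inputs.** n = 15 and alpha 0.05 are from the SAP; two-sided testing is assumed for two-condition contrasts. The unit is the within-subject residual SD. The documents give no session-effect size, so every shift s below is an assumption. The effect is set to give about 0.80 power, so that losses are visible.

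**Three conditions, starts 5/5/5, each condition equally often in each session.** Effects (d, d, 0) with d = 1.04.
- Numerator noncentrality: 15 × (2/3)d² = 10d² = 10.8.
- An omitted session effect adds denominator noncentrality: 15 × (2/3)s² = 10s² for a first-night shift, and 15 × 2s² = 30s² for a steady drift of s per session.
- Power comes from the doubly noncentral F(2, 28). With the term it is F(2, 26).

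| Assumed effect | Without term | With term | Null rejection without |
|---|---|---|---|
| none | 0.80 | 0.80 | 0.050 |
| first night 0.25 | 0.79 | 0.80 | 0.047 |
| first night 0.5 | 0.77 | 0.80 | 0.039 |
| first night 1 | 0.67 | 0.80 | 0.019 |
| drift 0.5 per session | 0.70 | 0.80 | 0.024 |
| drift 1 per session | 0.41 | 0.80 | 0.003 |

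**At the SAP's effect size.** Read as SDs of the difference, d = 1.2√2 = 1.70 residual SDs. The same formula gives 0.997, 0.996 and 0.990 without the term at first-night shifts of 0, 0.5 and 1, and 0.997 with it. At drifts of 0.5 and 1 it gives 0.99 and 0.95 without.

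**Two conditions, split 8:7.** The effect is 0.78 SDs of the difference.
- Numerator noncentrality: 15(0.78 ± s/(15√2))². Denominator: (s²/2)(15 − 1/15).
- Power without the term is 0.74 or 0.79 at s = 0.5, and 0.58 or 0.70 at s = 1, depending on the direction of the shift. With the term it is about 0.80.

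**Random losses, 15 kept from 30, later order by coin-flip (simulated).** Without the term: 0.80, 0.77, 0.67 at first-night shifts of 0, 0.5, 1. With it: 0.78 throughout. Break-even is near 0.4 SD. Omnibus null rejection without the term is 0.046 and 0.034 at 0.5 and 1.

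**When bias appears.**
- *Fixed later order (assumed).* Suppose the remaining conditions always followed the listed order: nested-single-sham, single-nested-sham, sham-nested-single. Mean session is (1+2+2)/3 = 1.67 for nested, 2.00 for single frequency and (3+3+1)/3 = 2.33 for sham. Nested minus sham is biased by 0.67 of the per-session drift in size, and omnibus null rejection is about 0.07 at 0.5 SD. A pure first-night shift gives no bias here, because starts are balanced.
- *Unequal analysed sequences.* At a realised 7/5/3 split of starts and a 1 SD first-night shift, the bias is (7 − 3)/15 = 0.27 SD, with pairwise alpha 0.063 and omnibus 0.040. A gap of 4 or more between start groups has probability 0.26 if 15 are kept at random from 10/10/10.

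**The case against.** The strongest case against acting has four parts.

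1. *The losses are shown at an effect smaller than the plan's.* This stands. Even with d = 1.2 read in residual SDs (numerator noncentrality 10 × 1.44 = 14.4), power without the term is 0.906, 0.885 and 0.814 at first-night shifts of 0, 0.5 and 1, so it stays above 80%. The secondary outcomes, including the memory tasks, use the same model but have no stated effect size, so the reassurance does not extend to them.
2. *The protocol measures before and after each train, and the memory tasks before and after sleep, so night effects cancel.* This stands if the change is what is analysed. The SAP does not commit to that for the primary outcome.
3. *The term can cost power.* This stands: 2 to 3 points under random losses with no session effect.
4. *Keeping exactly 15 of 30 is a harsh case.* Also fair. The surplus covers screening failures, some of which may precede allocation. With 24 of 30 kept, the chance of a gap of 4 or more falls from 0.26 to 0.12.

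In the other direction, a reader might infer that the comparisons with sham are biased or that type I error is inflated. The documents do not support this. The later order is unstated, not shown to be fixed or unbalanced, and computer-generated block randomisation is compatible with a random later order. Unequal sequences among analysed subjects are possible but not shown. Equally, a reader might take the cost to be precision in every case. That is too strong for the 18-50 branch, where it depends on the unstated order.

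**Conclusion.** The point holds as a cheap improvement of optional-to-moderate weight. With balanced or randomly ordered sequences, omitting period makes the test conservative. It costs about 3 points of power at an assumed 0.5 SD first-night shift and 13 at 1 SD, and more under a steady drift. In the two-condition branch at 8:7 the loss runs from about 1 to 6 points at 0.5 SD and 10 to 22 at 1 SD. These sizes rest on assumed session effects and on an effect tuned to 0.80 power. Under a first-night shift at the SAP's d = 1.2 on the difference scale, power is about 0.99 either way. Session effects are more plausible in the 18-50 branch, because the older adults' adaptation night already reduces a first-night effect. Bias is conditional on a fixed later order with drift, or on unequal analysed sequences, and neither is established.

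**What to change.** In both cross-over branches, analyse primary and secondary outcomes with condition and period as fixed effects and subject as random. Say for each outcome, including the word-pair and finger-tapping tasks, whether it is the after value or the before/after change.

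In the 18-50 branch, state the sequences. If allocation is still open, use position-balanced sequences, for example all six orders (30 enrolled is five blocks of six). Otherwise report the number analysed per sequence. The older-adult randomisation needs no change.

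The cost is one SAP line, plus a new randomisation list only if 18-50 allocation is open. Statistically:
- The term uses 1 to 2 residual degrees of freedom (28 to 26 with three conditions), which is negligible with balanced sequences: 0.803 to 0.799.
- With unequal sequences and no session effect it costs about 2 to 5 points: 0.80 to 0.78 on average under random losses, 0.80 to 0.75 at a 10:5 split.
- If later orders were in fact fixed as listed, the cost with no session effect is larger, about 0.80 to 0.61. Balancing the sequences therefore matters as well as the model.
- If every outcome is a before/after change, expect little gain.

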This will be a randomized-controlled trial with two study arms: a tACS treatment phase and a sham treatment phase. The subjects will be assigned to one of two treatment groups (tACS vs sham) in a 1:1 ratio using block randomization. Stimulation will be applied in-phase, single frequency or nested, if indicated based on the results of experiments 1 and 2. Computer-generated randomization will place each subject into one of the study groups. The primary outcome measured is EEG power of slow wave sleep of 0.5-2 Hz, measured immediately before and after each train of stimulation. To detect a significant change ($p<0.05$) of EEG power increase $\geq 20\%$ above sham, with a power of 0.80, a sample size of 30 subjects will be necessary. Subjects will receive either stimulation type, tACS or sham, each night for the one week study period, for up to 7 stimulation sessions pending results of Experiment 2. Subjects will have up to 24 weeks to complete all study sessions and complete the trial. The proposed study seeks to enroll 35 participants to account for participants that may fail our screening criteria, have unusable data or drop-out of the study before completion.

Secondary outcomes will include analysis of slow wave EEG coherence, slow and fast spindle activity, duration of slow wave sleep, total duration of sleep, and subjective sleep quality reported on the Consensus Sleep Diary (CSD), Pittsburgh Sleep Quality Index (PSQI), mood assessment by the Hospital Anxiety and Depression Scale (HADS), overall function in the Clinical Global Impression of Change (CGIC).

Consensus Sleep Diary (CSD)

The CSD is a sleep journal instrument that is designed to measure sleep and has been validated for intervention trials in insomnia (38, 41).

Word Paired-Associate Task

Our computerized paired-associate task consists of 48 semantically related words selected from a normative database with assessment of memory encoding on recollection performance (25, 42)

Finger Tapping Task

This is a finger sequence tapping task of procedural memory. Subjects repeatedly finger-tap with their non-dominant hand a five-element sequence presented on a computer monitor, e.g. 4-2-3-1-4, as fast and accurately as possible on a key board (7).

Pittsburgh Sleep Quality Index (PSQI)

This is a 10 question questionnaire consisting of questions related to usual sleep habits (39).

The Hospital Anxiety and Depression Scale (HADS)

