Total time		60 minutes

HOME PORTION- ADAPTATION NIGHT

Name of Instrument/tool/procedure	Purpose (i.e. what data is being collected)	Time to complete
EEG Recording	Gather EEG data before and after stimulation	overnight
Complete Consensus Sleep Diary	Assess Sleep Quality (after each night of study)	10 minutes
Total time		Overnight

HOME PORTIONS-tACS TREATMENT NIGHTS

Name of Instrument/tool/procedure	Purpose (i.e. what data is being collected)	Time to complete
tACS/EEG Stimulation and Recording	Gather EEG data before and after stimulation	overnight
Complete Consensus Sleep Diary	Assess Sleep Quality (after each night of study)	10 minutes
Word Paired-Associate Task	Assess Memory Encoding (before and after sleep)	20 minutes
Finger Tapping Task	Assess Procedural Memory (before and after sleep)	15 minutes
Total time		Overnight x 3 nights (1 week apart for washout)

VISITS TWO, FOUR, and SIX

Name of Instrument/tool/procedure	Purpose (i.e. what data is being collected)	Time to complete
Post-procedure questionnaire	Assess for tolerability of device and address any safety concerns	15 minutes
Collection of Sleep Diary and Equipment	Collect and Inventory Instruments and Hardware	15 minutes
Total time		30 minutes

VISITS THREE, and FIVE

Name of Instrument/tool/procedure	Purpose (i.e. what data is being collected)	Time to complete
EEG/tACS Equipment Distribution	Ensure subjects remember proper equipment use	20 minutes
Total time		20 minutes

5. tACS SLEEP MODULATION MCI EXPERIMENT

INITIAL VISIT

Name of Instrument/tool/procedure	Purpose (i.e. what data is being collected)	Time to complete
Gather informed consent/UBACC	Gather consent/Screen for capacity	15 minutes
EEG/tACS Equipment Trial	Teach subjects proper equipment use/adjust for comfort	45 minutes
HADS	Assess anxiety and depression (to be administered for MCI trial)	5 minutes
CGIC	Assess Global Impression (to be administered for MCI trial)	5 minutes
Total time		60-70 minutes

HOME PORTIONS

Name of Instrument/tool/procedure	Purpose (i.e. what data is being collected)	Time to complete
tDCS/EEG Stimulation and Recording	Gather EEG data before and after stimulation	overnight
Complete Consensus Sleep Diary	Assess Sleep Quality (after each night of study)	10 minutes

Word Paired-Associate Task	Assess Memory Encoding (before and after sleep each night)	20 minutes
Finger Tapping Task	Assess Procedural Memory (before and after sleep)	15 minutes
Total time		Overnight x 7 nights

VISITS TWO, FOUR and SIX

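### Protocol and SAP word the primary 0.5-2 Hz comparison differently, neither defines it fully, and the lead test as written makes no use of the recorded pre-stimulation EEG, which matters mainly in the parallel MCI trial

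*SAP*

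**What the plan says.** **Protocol, section IV.3 (healthy 18-50) and IV.4 (older adults).** Both crossover branches use the same sentence: "The primary outcome measure is induced EEG power of slow wave sleep of 0.5-2 Hz measured immediately before and after each train of stimulation".

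**Protocol, section IV.5 (MCI).** The wording is nearly the same: "The primary outcome measured is EEG power of slow wave sleep of 0.5-2 Hz, measured immediately before and after each train of stimulation". The design is not a crossover: "The subjects will be assigned to one of two treatment groups (tACS vs sham) in a 1:1 ratio using block randomization". Treatment is repeated: "Subjects will receive either stimulation type, tACS or sham, each night for the one week study period, for up to 7 stimulation sessions".

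All three branches set the sample size for an increase in EEG power of at least 20% above sham. No branch says whether the analysed quantity is post-train power, a difference, a ratio or an adjusted post value, or how trains and nights are reduced to one value per subject.

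**Protocol, section XII.5 (MCI home portions).** Pre-stimulation EEG is collected: "Gather EEG data before and after stimulation".

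**SAP.** The design is stated once for everything: "For each arm, we will perform a three-arm cross-over design". The lead test, and the only one with a power statement, compares conditions "as measured in EEG power in 0.5-2 Hz frequency following tES using repeated measures ANOVA". The secondary list includes "changes in slow wave coherence, changes in slow wave power". The SAP does not use the word primary.

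**The concern.** The protocol describes a pair of measurements around each train. The SAP powers a test of what follows stimulation and mentions change only as secondary. A statistician holding both documents could defend post-only power, a pre-to-post change, or baseline-adjusted post power as the primary analysis, and could make that choice after seeing the data. The choice matters because the three have different power in the same trial.

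It matters most in MCI. In the two crossover branches each subject is his or her own control, so a repeated measures analysis already removes stable differences in slow wave power between people. In a parallel comparison those differences stay in the error term unless a baseline is used. The baseline is already being recorded.

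**Working it through.** **The plan's own figure.** The SAP states 15 subjects, d = 1.2, 80% power and significance 0.05. Take three conditions in a repeated measures ANOVA, with 1.2 as the range of the means, the middle mean at the midpoint and zero within-subject correlation. Then f = 1.2 × √(1/6) = 0.490, noncentrality = 15 × 3 × 0.490² = 10.8, df 2 and 28, and power = 80.2%. The figure reproduces on these assumptions with no baseline term, but for a three-condition crossover, not for a two-arm parallel comparison.

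**MCI inputs.** From the documents: 30 subjects at 1:1, so 15 per arm; significance 0.05. Assumed: two-sided test; a two-arm comparison (the SAP states none for MCI); equal pre and post SDs; correlation r between the baseline and the analysed value. The documents give neither SD nor r, so r is varied. Two effects are used: d = 1.06, chosen to give 80.0% post-only, and the SAP's d = 1.2.

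**Formulas.**
- Post-only: two-sample t, noncentrality d × √(15/2), df 28. For d = 1.06 this is 1.06 × 2.739 = 2.90.
- Change score: variance 2(1 − r), so d becomes d / √(2(1 − r)), df 28.
- Baseline-adjusted: residual variance 1 − r², df 27, simulated with a random covariate so that chance imbalance is counted.

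| Analysis | r = 0 | r = 0.3 | r = 0.5 | r = 0.7 |
|---|---|---|---|---|
| d = 1.06, post-only | 80.0% | 80.0% | 80.0% | 80.0% |
| d = 1.06, change | 50.9% | 65.9% | 80.0% | 95.1% |
| d = 1.06, adjusted | 78.5% | 82.1% | 88.7% | 97.0% |
| d = 1.2, post-only | 88.7% | 88.7% | 88.7% | 88.7% |
| d = 1.2, change | 61.2% | 76.5% | 88.7% | 98.4% |
| d = 1.2, adjusted | 87.4% | 90.3% | 94.8% | 99.1% |

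Adjustment breaks even with post-only at r of about 0.2 (d = 1.06: 79.3% at r = 0.15, 80.2% at r = 0.20). A change score breaks even at r = 0.5. That threshold needs equal SDs; in general it is half the ratio of the pre SD to the post SD.

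**Which baseline.** MCI subjects are stimulated on up to seven nights, and Specific Aim 4 concerns cumulative effects. Every pre-train window after the first train therefore follows stimulation. If such a window already carries half the effect (assumed), the adjusted effect is 1 − 0.5r of the total: 85%, 75% and 65% at r = 0.3, 0.5 and 0.7. Power at d = 1.06 is then 66%, 63% and 68%, below the unadjusted 80.0%. Only the window before the first train of the first night precedes all stimulation.

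**Crossovers.** For a paired comparison of two conditions with n = 15 and a standardized paired difference of 0.778 (chosen for 80%), regressing the post difference on the pre difference (df 13) gives 76.5%, 80.3% and 87.1% at night-level correlations of 0, 0.3 and 0.5. Break-even is about 0.3. This matches the two-condition older-adult branch and is only a guide for the three-condition branch.

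**The case against.** Several points on the other side are sound.

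- **The contrast is partly stated.** Before-and-after measurement together with an increase of at least 20% above sham points towards a pre-to-post rise compared with sham. It does not settle the matter: post-train power 20% above the sham level fits the same words.
- **The SAP does not rule out a baseline.** A pre/post factor could sit inside its repeated measures ANOVA. It is unstated, not excluded.
- **The secondary item is vague.** A reader might infer that the SAP has moved the protocol's primary outcome into the secondary list. The text does not support that. The protocol never defines its primary as change, and the SAP does not say that its changes in slow wave power are same-train pre/post differences.
- **Validity is not in question.** A reader might also infer that a test without baseline is biased. Under randomization it is not; only precision and clarity are at stake.
- **The gain is uncertain.** A first-night baseline is one window, and the MCI branch describes no adaptation night. Its correlation with a seven-night summary could be low. At d = 1.2 and r = 0.3 the gain is only 1.6 points (88.7% to 90.3%).

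What remains is that the two documents describe the main comparison in different words, neither defines it fully, and the lead test as written leaves recorded information unused in the one randomized branch where subjects are not their own controls.

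**Conclusion.** The point holds as an unreconciled, incompletely defined primary endpoint and a missed gain in precision in MCI. It should be corrected. The mismatch in wording rests on the texts alone and needs no assumption.

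The size is illustrative. With 15 per arm, two-sided 0.05, equal SDs and d = 1.06, adjustment moves MCI power from 80.0% to about 78.5%, 82%, 89% and 97% at r = 0, 0.3, 0.5 and 0.7. Below r of about 0.2 there is no gain. At the SAP's d = 1.2, the choice among the three analyses moves power between 61.2% and 99.1% over the same range of r. Whether 30 MCI subjects are enough for a 20% increase cannot be checked, because no SD is given. In the crossovers the case is for consistent wording only.

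**What to change.** 1. State one primary endpoint in the same words in the protocol and the SAP. Say whether it is post-only, change or baseline-adjusted, and how trains and nights become one value per subject, for example the mean of log post-train 0.5-2 Hz power over all trains and nights. The log scale fits a target expressed as a percentage.
2. For MCI, first replace the three-arm crossover wording in the SAP with a two-arm comparison. Then compare that value between arms with log pre-stimulation power as covariate, taken before the first train of the first night. Keep same-train pre/post change as a secondary analysis, and say openly that this refines the protocol's wording.
3. In the crossovers, reconcile the wording. Baseline adjustment is optional there; decide on it in advance.

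**Cost.** Text changes in two documents and no new data. In MCI, about 1.5 points of power if the baseline is uninformative (78.5% against 80.0% at d = 1.06; 87.4% against 88.7% at d = 1.2), and no gain below r of about 0.2, which is possible with a single first-night window. In a crossover, optional adjustment could lose about 4 points (76.5% against 80%).
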